A total of 1107 patients will be enrolled in the study(41 clusters, 27 patients in each cluster). With 40(20 per treatment group) clusters randomized at a 1:1 ratio (Intervention group: control group) and a size of 27 individuals per cluster (21 after drop out, assuming 20% drop out), approximately 1080 patients will be enrolled from the 40 randomized hospitals. In addition, the leading site will be assigned to the intervention group without following the randomization procedure and approximately 27 individuals will be enrolled. Whilst, data from the leading site will be excluded from the primary analysis set.

If the true hazard ratio (HR) for the comparison of QS versus Usual Care group in this patient population is 0.70, assuming ICC is 0.079 (ICC of 0.079 was estimated using analysis of variance method based on results from a pilot study¹⁰), 713 CID events will provide 80% power to demonstrate a statistically significant difference in CID free duration at a 5% 2-sided significance level (this could translate to an increase of median time to CID from 121 days to 172 days), assuming CID free duration is exponentially distributed.

Methods for statistical analyses

Descriptive statistics will be calculated, including n, means, standard deviations, medians, and interquartile ranges for continuous variables and frequency counts and percentages for categorical variables. Percentage will be calculated based on non-missing data unless otherwise specified. Data will be examined for skewness, outliers, and systematic missing data. Transformations will be undertaken as needed. All statistical procedures will be conducted using SAS version 9.4 or later, while graphs may also be produced using R.

The primary outcome measure is time to CID. The primary outcome analysis will be based on FAS, which includes all enrolled subjects among all randomized hospitals who had at least one post-baseline efficacy data assessments. Comparison between treatment groups will be

conducted using a clustered log-rank test at two-sided significance level of 0.05. Kaplan-Meier curve of time to CID will also be presented by treatment group.

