3. METHODOLOGY

3.1 Study Design

This is a interventional, cluster-randomized, pragmatic clinical study. Totally, there are 41 sites will be selected across China, It is worth mentioning that leading site will directly enter the intervention group, mainly be in charge of supervising and managing the QS implementation in the sites of intervention group. The rest 40 sites will be randomized (stratified by tier levels and geographic region) to the intervention group or control group at the ratio of 1:1. In the intervention group, QS implementation will be performed, and will be checked every 12 weeks. The control group will maintain the current practice. Eligible patients will be recruited and followed up every 12 weeks for 48 weeks.

Eligible consented patients will be enrolled consecutively to minimize selection bias (see section 3.3.2 and section 3.3.3 for inclusion and exclusion criteria).

Figure 1. study schematic

Leading site will directly enter the intervention group, and will recruit at least 27 patients, supervises and manages the QS implementation in the sites of intervention group.

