5.2 Sample size

A total of 1107 patients will be enrolled in the study(41 clusters, 27 patients in each cluster). With 40(20 per treatment group) clusters randomized at a 1:1 ratio (Intervention group: control group) and a size of 27 individuals per cluster (21 after drop out, assuming 20% drop out), approximately 1080 patients will be enrolled **from the 40 randomized hospitals**. In addition, the leading site will be assigned to the intervention group without following the randomization procedure and approximately 27 individuals will be enrolled. **Whilst, data from the leading site will be excluded from the primary analysis set.** The hypotheses are:

$$H_0: S_1(t) = S_2(t) \quad \text{for all } t$$

$$H_1: S_1(t) \neq S_2(t) \quad \text{for some } t$$

If the hazard ratio (HR) for the comparison of QS versus usual care in this patient population is 0.70, assuming ICC is 0.079, 713CID events will provide 80% power to demonstrate a statistically significant difference at a 5% 2-sided significance level (this could translate to an increase of median time to CID from 121 days to 172 days), assuming CID free duration is exponentially distributed.

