5.3 Methods for statistical analyses

5.3.1 General Considerations

The statistical analysis plan (SAP) will be finalised prior to data base lock (DBL) and it will include a more technical and detailed description of the statistical analyses described in this section. As randomisation was at the hospital (cluster) level, appropriate statistical methods to account for the clustering effect will be used in the analysis.

Descriptive statistics will be calculated, including n, means, standard deviations, medians, and interquartile ranges for continuous variables and frequency counts and percentages for categorical variables. Percentage will be calculated based on non-missing data unless otherwise specified.

Unless otherwise specified, analyses of change from baseline to a particular time point will be based on the measurement available at that time point. Missing data will be assumed missing at random or missing completely at random. In general, no imputation will be applied unless otherwise specified.

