5.3.2 Analysis of the primary variable (s)

The primary outcome measure is time to CID, which is defined as from enrolment to CID. CID is defined as the first occurrence of any following events over study follow-up:

- ≥ 100 mL decrease in pre-dose trough FEV1
- One moderate-to-severe COPD exacerbation occurring after enrolment
- ≥ 2 -unit increase in CAT total score

Patients who are CID free and alive at the time of analysis will be censored at the date of their last follow-up assessments. Patients who died prior to CID will be censored at the date of death. Patients who withdrew from the study without experiencing an event will be censored at the date of withdrawal.

Time to CID will be analysed using a clustered log-rank test for generation of the p-value and using Breslow approach for handling ties. Hazard Ratio and regarding 95% CI will also be presented. Statistical testing will be conducted at significance level of 0.05.

For each treatment group, time to CID will be summarized using K-M (Kaplan-Meier) method and K-M curves will also be presented.

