5.3.3 Analysis of the secondary variable(s)

Change from baseline in trough FEV1, CAT over 48 weeks and rate of moderate/severe and severe COPD exacerbation

Change from baseline in trough FEV1, CAT over 48 weeks will be analysed using a random effects model. The model is planned to take clusters as random intercept term, with covariates including but not limited to: tier of hospital, geographic regions, COPD exacerbation history at baseline, CAT at baseline, trough FEV1 at baseline, etc. For the covariance structure within subject, the unstructured (UN), Toeplitz (TOEP), first-order autoregressive (AR(1)) or compound symmetric (CS) covariance structure will be used. The unstructured (UN) covariance will be used firstly. If there is convergence problem under current covariance structure, the latter structure will be used as the order presented above until no convergence problem. Estimated effect size (mean difference between the two treatment groups) and regarding 95% confidence interval will be provided, while nominal p-value will also be presented as appropriate.

Rate of moderate or severe COPD exacerbation and severe COPD exacerbation will be analysed using random effects Poisson regression. Chronic obstructive pulmonary disease exacerbations will be considered separate events provided that 7 or more days are between the recorded stop date of the earlier event and start date of the latter. Time at risk of experiencing an exacerbation will be used as an offset variable in the model. The model might include but not limited to below covariates: tier of hospital at baseline, geographic regions, baseline COPD exacerbation history, baseline CAT and baseline trough FEV1. Estimated relative risk with 95% confidence interval will be provided where nominal p-value will be presented as appropriate as well.

Proportion of patients received at least once inhalation technique review, proportion of patients received long-acting inhaled medicine with percentage of days covered (PDC)≥ 80% over 48 weeks and treatment pattern in intervention group and control group

The other secondary outcome measures are:

Proportion of patients received inhalation technique review at least once during follow-up period, where denominator will be number of patients with available record in FAS at 12weeks/24weeks/36weeks/48weeks.

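### The only confirmatory test, a clustered log-rank, uses neither the randomisation strata nor baseline values: valid, but conservative if tier and region predict CID, and open to measured recruitment imbalance

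*Protocol*

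**What the plan says.** Section 3.1 of the protocol has 40 hospitals "randomized (stratified by tier levels and geographic region) to the intervention group or control group". Section 5.4.1 plans eight hospitals in each of five regions and lists tier and region among the potential sources of difference between hospitals. It does not say that they predict CID.

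For the primary endpoint, section 5.3.2 says: "Time to CID will be analysed using a clustered log-rank test for generation of the p-value". The synopsis agrees: the comparison is to be "conducted using a clustered log-rank test at two-sided significance level of 0.05". Neither place names strata or covariates. Section 5.3.2 adds: "Hazard Ratio and regarding 95% CI will also be presented", without naming the model behind it. Section 5.4.2 gives this one analysis the whole 5% alpha.

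Section 5.3.3 treats the exploratory endpoints differently. The FEV1 and CAT models have "covariates including but not limited to: tier of hospital, geographic regions, COPD exacerbation history at baseline, CAT at baseline, trough FEV1 at baseline". For the exacerbation rates: "The model might include but not limited to below covariates: tier of hospital at baseline, geographic regions, baseline COPD exacerbation history", together with baseline CAT and FEV1.

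Section 5.3.1 says of the SAP that "it will include a more technical and detailed description of the statistical analyses described in this section". The one sensitivity analysis (5.3.4) changes the analysis set, not the method.

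**The concern.** Two limited points follow.

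1. **Efficiency.** Allocation within strata removes differences between strata from the treatment contrast. A variance computed without the strata still contains them. If tier and region are prognostic, the standard error is too large, the true type I error falls below 5%, and power is given up.
2. **Recruitment.** Section 3.2.2.2 has the initial QS training and test before a site launches, so intervention hospitals enrol patients knowing their arm. One exclusion (3.3.3) rests on the investigator's judgement. Consecutive enrolment (3.1) and screening records (3.3.4) limit imbalance, but an unadjusted test corrects none of what remains.

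At stake is the one p-value that decides the trial. The variables that would help are already collected at Visit 0 (Table 1) or known from randomisation.

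**Working it through.** **The plan's own figure.** Section 5.2 states: "assuming ICC is 0.079, 713CID events will provide 80% power" at HR 0.70. Schoenfeld's formula gives 4 × (1.96 + 0.8416)² / (ln 0.70)² = 247 events without clustering; Freedman's gives 253. With design effect 1 + (m − 1) × 0.079:

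- m = 21: 2.58, so 638 or 653 events
- m = 27: 3.054, so 755 or 773 events

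The figure of 713 corresponds to m of about 24-25, which is not stated. That is a separate matter. The check below takes the stated 80% power as given.

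**Closed form.** Inputs: ICC 0.079, 27 per hospital, 80% power (section 5.2). Assumed: a share f of between-hospital variance is due to tier and region. The design effect splits as 0.921 + 27 × 0.079 = 3.054. Stratified allocation shrinks the true variance of the contrast by

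r = (0.921 + 27 × 0.079 × (1 − f)) / 3.054.

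The stated test still uses the unshrunk variance, so:

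- stated power = Φ(0.8416/√r)
- adjusted power = Φ(2.8016/√r − 1.96), before loss of degrees of freedom
- type I error of the stated test = 2 × (1 − Φ(1.96/√r))

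| f | r | Stated power | Adjusted power | Type I error, stated |
|---|---|---|---|---|
| 10% | 0.930 | 80.9% | 82.8% | 4.2% |
| 25% | 0.825 | 82.3% | 86.9% | 3.1% |
| 50% | 0.651 | 85.2% | 93.5% | 1.5% |

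**Simulation of the design.** Settings: five regions × eight hospitals; tier split assumed 4:4; 27 patients each; 20% dropout; control median 121 days; 336 days of follow-up; conditional HR 0.70; between-hospital log-hazard variance 0.12; about 790 events. Baseline covariates are non-prognostic here, so any gain comes from the strata alone. The Cox model uses a clustered sandwich variance × 40/33 and t with 33 df. There were 5000 runs per cell, with Monte Carlo error about 0.6 points for power and 0.3 for type I error.

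| f | Stated | Adjusted Cox | Within-stratum permutation | Type I error, stated / Cox |
|---|---|---|---|---|
| 0% | 75.0 | 74.0 | 73.4 | 5.8 / 5.4 |
| 5% | 77.7 | 77.4 | 76.8 | – |
| 10% | 77.3 | 78.2 | 77.5 | 4.6 / 4.8 |
| 15% | 77.4 | 79.9 | 79.3 | – |
| 25% | 78.7 | 83.1 | 82.4 | 3.4 / 4.7 |
| 50% | 80.6 | 90.8 | 90.3 | 1.6 / 5.6 |

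The shortfall from 80% at f = 0 is attenuation of the marginal HR, not missing strata. With a conditional HR of 0.686, the stated test has 80.3% and Cox 79.4% at f = 0, and 82.6 against 87.0% at f = 25%.

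The Cox gain depends on which variance form the clustered log-rank uses: −1.0 to +0.6 points at 0%, +2.5 to +6.8 at 25%, +8.3 to +12.3 at 50%. It is −2.8 at 0% against an uncorrected arm-specific variance, whose type I error there is 6.7%. A 2:6 tier split changes little (79.1 vs 83.3 at 25%; 79.1 vs 89.7 at 50%).

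A second simulation, with between-hospital variance 0.10 and cluster-level adjusted tests, gives 81-83 vs 80% at f = 0, 83-85 vs 86-87% at 25%, and 86-87 vs 93% at 50%. The pattern also holds when 60% of events are tied to the 12-week visits.

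**Recruitment imbalance.** No true effect, f = 25%, assumed shift in a prognostic baseline covariate, covariate HR 1.22 or 1.35 per SD:

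- shift 0.2 SD: stated test rejects 4.5 or 5.7%
- shift 0.4 SD: stated test rejects 6.8 or 11.9%
- adjusted for strata and covariate: 3.7-5.2% throughout
- strata without the covariate, shift 0.4 SD: 9.4 or 15.1%

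The last line shows that strata and baseline values belong together: part of the bias in the stated test is masked by its conservatism. Consistent with this, a simulation with no stratum effect and covariate log HR 0.3 per SD (1000 runs) rejects 9-13% unadjusted at 0.2-0.3 SD, against 6-7% adjusted.

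**The case against.** The strongest reply is that this argues from silence. The protocol never says the test is unstratified, the SAP is not shown, and a clustered log-rank stratified by tier and region is still a clustered log-rank. A log-rank test takes no covariates by nature, so the contrast with section 5.3.3 is no contradiction. The stated test is valid and loses nothing against plan: its own power does not fall as the strata become more prognostic. The variance share is assumed, 50% has no support in the documents, and imbalance of 0.2 SD does little harm in the main simulation. An adjusted Cox model targets a conditional HR and adds a proportional-hazards assumption.

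Much of this stands. The point is one of efficiency and robustness, not error. The gain is conditional and of unknown size, and below a share of about 6-10% adjustment gains nothing. The SAP could add strata, which limits the severity.

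It does not dispose of the point. Section 5.3.2 fixes the method down to the handling of ties, section 5.3.1 promises more detail on the analyses described rather than other ones, and baseline adjustment would change the stated test. The permutation option keeps a log-rank-type test and needs no proportional-hazards assumption for its p-value.

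**Conclusion.** The concern holds as a conditional, inexpensive improvement that should be made. The stated test is valid in the usual approximate sense, provided recruitment does not differ by arm; with 40 clusters and a normal reference it is slightly liberal (5.8% simulated) when the strata carry no prognosis. If tier and region explain 25% of between-hospital variance, its type I error is about 3-4% and adjustment adds about 2.5-7 power points. At 50% the figures are about 2% and 8-12 points in the main simulation. If they explain nothing, adjustment costs about 1-2 points.

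These sizes rest on an assumed variance share, tier split and exponential hazards. Protection against recruitment imbalance matters mainly for larger shifts and covers measured variables only. Confidence is medium, because the documents give neither the share nor any sign of how large an imbalance might be.

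**What to change.** Before database lock and before any comparison by arm, prespecify that the primary p-value and HR account for tier and region and, preferably, baseline FEV1, CAT and exacerbation history, by one of:

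- **(a)** permuting hospitals within the randomisation strata on a covariate-adjusted log-rank statistic. This must follow the actual allocation scheme and say how a backup hospital that replaces a withdrawn one (5.4.1) enters the permutation; or
- **(b)** a marginal Cox model with hospital-clustered, small-sample-corrected standard errors and a t reference.

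Do not use an uncorrected within-stratum sandwich variance, since each stratum holds few hospitals. Name the model that gives the HR. Report the unadjusted clustered log-rank test and the Kaplan-Meier curves as supportive.

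State how missing baseline covariates are handled, so that no FAS patient is dropped. CAT and exacerbation history are entry criteria (3.3.2), so mainly FEV1 can be missing; mean fill plus a missing indicator is enough. With 10% missing FEV1, three covariates at HR 1.22 per SD and f = 25%, power is 75.7% for the stated test and 82.5% for Cox. Section 4.1.1 defines trough FEV1 only for weeks 12-48, so name as covariate the same baseline FEV1 that serves as reference for the 100 mL criterion.

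The cost is wording, with no new data. If the change counts as substantial, section 8.5 requires an amendment with Ethics Committee approval. The statistical costs are a few degrees of freedom among 40 hospitals, about 1-2 power points if the strata are not prognostic, an HR conditional on covariates, and proportional hazards under option (b).

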5.3.3 Analysis of the secondary variable(s)

Change from baseline in trough FEV1, CAT over 48 weeks and rate of moderate/severe and severe COPD exacerbation

Change from baseline in trough FEV1, CAT over 48 weeks will be analysed using a random effects model. The model is planned to take clusters as random intercept term, with covariates including but not limited to: tier of hospital, geographic regions, COPD exacerbation history at baseline, CAT at baseline, trough FEV1 at baseline, etc. For the covariance structure within subject, the unstructured (UN), Toeplitz (TOEP), first-order autoregressive (AR(1)) or compound symmetric (CS) covariance structure will be used. The unstructured (UN) covariance will be used firstly. If there is convergence problem under current covariance structure, the latter structure will be used as the order presented above until no convergence problem. Estimated effect size (mean difference between the two treatment groups) and regarding 95% confidence interval will be provided, while nominal p-value will also be presented as appropriate.

Rate of moderate or severe COPD exacerbation and severe COPD exacerbation will be analysed using random effects Poisson regression. Chronic obstructive pulmonary disease exacerbations will be considered separate events provided that 7 or more days are between the recorded stop date of the earlier event and start date of the latter. Time at risk of experiencing an exacerbation will be used as an offset variable in the model. The model might include but not limited to below covariates: tier of hospital at baseline, geographic regions, baseline COPD exacerbation history, baseline CAT and baseline trough FEV1. Estimated relative risk with 95% confidence interval will be provided where nominal p-value will be presented as appropriate as well.

Proportion of patients received at least once inhalation technique review, proportion of patients received long-acting inhaled medicine with percentage of days covered (PDC)≥ 80% over 48 weeks and treatment pattern in intervention group and control group

The other secondary outcome measures are:

Proportion of patients received inhalation technique review at least once during follow-up period, where denominator will be number of patients with available record in FAS at 12weeks/24weeks/36weeks/48weeks.

Proportion of patients received long-acting inhaled medicine with percentage of days covered (PDC)≥ 80% over 48 weeks, where denominator will be based on patients with long-acting inhaled medicine records at baseline or through the study follow-up.

Proportion of patients prescribed inhaled maintenance medicine at 12 weeks/24 weeks/36 weeks/48 weeks and proportion of patients prescribed COPD-related medicine at 12 weeks/24 weeks/36 weeks/48 weeks will be derived based on number of patients with available records respectively.

All above four outcome measures will be summarized using descriptive statistics by treatment group.

5.3.4 Sensitivity analysis

Sensitivity analysis will be conducted among all enrolled subjects who had at least one post-baseline efficacy data assessments.

5.4 Bias

5.4.1 Methods to Minimise Bias

Potential sources of bias come from differences between hospitals, which includes participation in different tiers and different geographic regions, differences in the capability of COPD management exist between the same tier hospital in different cities. There may be a selection bias that occurs because the hospitals need to meet the inclusion criteria in order to participate in the study. However, clustered randomization, with every attempt to balance the

hospital tiers and geographic regions within each group, will somewhat equalize these medical centers across both study groups, to mitigate this bias. Additionally, an extra backup hospital will be selected in each strata to minimize selection bias. If a hospital withdraw from the study after randomization, the backup hospital in the corresponding strata will replace it.

Periodic collection of relevant data in the control group will improve the compliance of patients, to a certain extent, that will affect the HCP's attention to patients.

However, an independent team (a nurse from each site who will not be involved in recruitment and training) will be supposed to collect data in both groups to reduce and to balance the influence between data collection and the purpose for the study.

Potential cross-contamination across groups from patients transfer to different hospitals. In order to reduce contamination, the QIP study will choose 8 hospitals in each region. Hospitals will be selected from five regions of the whole country, namely, east, west, north, south and central. In addition, it will be emphasized in ICF and try to encourage patients to seek care at the study hospital if they need.

5.4.2 Adjustment for Multiple Comparisons

Only the analysis of primary outcome measure will be formal statistical testing with full portion of the alpha (0.05) assigned. All other comparisons will be exploratory and p-values will be nominal.

